Appendix

A.....Error!		
Bookmark not defined.			
Data	and	Safety	Monitoring
Plan.....Error! Bookmark not defined.		
Appendix B.....34		
DSMP Sample Study Report Outline.....34		

List of Abbreviations

LIST OF ABBREVIATIONS

AE	Adverse Event/Adverse Experience
AF	Atrial Fibrillation
CFR	Code of Federal Regulations
CRF	Case Report Form
FDA	Food and Drug Administration
GCP	Good Clinical Practice
HIPAA	Health Insurance Portability and Accountability Act
IB	Investigator's Brochure
IND	Investigational New Drug Application
IRB	Institutional Review Board
PHI	Protected Health Information
PI	Principal Investigator
SAE	Serious Adverse Event/Serious Adverse Experience
SOP	Standard Operating Procedure
VT	Ventricular Tachycardia

1. Study Summary

Title	Ultra-High Dose Diuretic Strategy for Management of Acute Decompensated Heart Failure-A Randomized, Double-Blind Pilot Trial
Running Title	Ultra-High Dose Diuretics for Heart Failure
Protocol Number	23-005262
Phase	Phase: 2
Methodology	Randomized, parallel-group clinical trial in acute decompensated heart failure patients with volume overload (requiring hospitalization) Group 1: Ultra high dose intervention with intravenous bumetanide 12.5 mg bid over 24 hours Group 2: Standard dose intervention with intravenous furosemide as twice the home dose of oral diuretic in furosemide equivalents bid over 24 hours
Overall Study Duration	12 months
Subject Participation Duration	Approximately 24 hours
Single or Multi-Site	Single Site-Mayo Clinic Rochester, MN
Objectives	To determine the safety and efficacy of ultrahigh dose diuretics compared to standard dose diuretics over 24 hours in patients with decompensated heart failure
Number of Subjects	20 patients total
Diagnosis and Main Inclusion Criteria	We will include patients with decompensated heart failure requiring hospitalization for intravenous diuresis regardless of ejection fraction.
Study Product, Dose, Route, Regimen	Patients will be randomized 1:1 to ultra-high dose (IV bumetanide 12.5 mg bid) vs standard dose (IV furosemide as twice the home dose of oral daily diuretic in furosemide equivalents administered bid) for 24 hours. Participants will undergo comprehensive physiological assessment at baseline and 24 hours with short Iohexol clearance for true glomerular filtration rate, apnea hypopnea index, electrocardiography, echocardiography, serum, and urine biomarkers. Patients will be monitored for side effects including muscle cramps, new onset atrial fibrillation (AF), sustained ventricular tachycardia (VT), symptomatic hypotension (MAP<60 or systolic blood pressure <80 mmHg), development of renal insufficiency and dialysis initiation.
Duration of Administration	Patients will be on therapy for 24 hours.

Statistical Methodology	The primary efficacy endpoint is urine output over 24 hours which will be compared by T test between the two groups. Primary safety endpoint will be incident decline in creatinine estimated glomerular filtration rate by 50% over 24 hours. Key secondary endpoints include weight change, NT-proBNP change, urine output, urine sodium excretion, creatinine, and cystatin C estimated GFR changes, apnea-hypopnea index, Iohexol glomerular filtration rate, serum and urine proteomic analyses, peripheral vein pressure and echocardiographic changes over 24 hours, estimated GFR at day 7 or discharge (whichever is sooner) will each be compared by T test between the two groups.
-------------------------	---

3. STUDY OBJECTIVES

3.1 Primary Objective

The primary objective of this trial is to demonstrate the superiority of ultrahigh dose diuretics compared to conventional diuretic strategies in terms of urine output at 24 hours.

3.2 Secondary Objectives

The secondary objectives of this study are

- a) To demonstrate safety of ultrahigh dose diuretics at 24 hours defined as development of renal insufficiency (creatinine estimated GFR decline of 50%), and hypotension (symptomatic MAP<60 or systolic blood pressure <80 mmHg).
- b) To determine mechanistic changes in cardiac function, sleep parameters and biomarker changes in response to ultrahigh dose diuretics compared to standard dose diuretics.
- c) To compare 24 hour change creatinine and cystatin C based changes in GFR with gold standard Iohexol clearance testing of GFR among the two diuretic strategies

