In this pilot study we will therefore compare an ultra-high diuretic strategy with a conventional diuretic strategy in patients with decompensated heart failure with a primary efficacy end point of urine output at 24 hours. The primary safety endpoint will be a decline in serum creatinine estimated GFR by 50% of baseline value at 24 hours. This will be a double-blinded randomized pilot trial of ultra-high dose diuretics (IV bumetanide 12.5 mg bid for 24 hours vs IV furosemide at usual doses (twice the home dose of oral daily diuretic in furosemide equivalents administered bid). New initiation of adjunct diuretics (thiazide, SGLT2 inhibitors, acetazolamide, and spironolactone) will be discouraged during the 24-hour study period. Key secondary endpoints include weight change, NT-proBNP change, urine output, urine sodium excretion, creatinine, and cystatin C estimated GFR changes, apnea-hypopnea index, iohexol glomerular filtration rate, serum and urine proteomic analyses, peripheral vein pressure and echocardiographic changes over 24 hours, estimated GFR at day 7 or discharge (whichever is sooner) will each be compared by T test between the two groups.

4.2 Hypothesis:

Ultrahigh dose diuretic infusion will be associated with greater diuretic response and will not be associated with clinically significant decline in eGFR over 24 hours (defined as decline in creatinine estimated GFR of 50% from baseline at 24 hours).

4.3 Innovation:

1. Ultra-high dose diuretic strategies have not been compared to conventional diuretic strategies in a randomized trial
2. The use of a double-blind strategy will minimize bias in terms of diuretic adjustment and alternative therapies.
3. The measurement of serum and urine biomarkers of renal injury, peripheral vein pressure and echocardiography changes at baseline and at 24 hours will provide novel insight into the hemodynamic, renal, and cardiac response to decongestion.

4. The relationship between creatinine based GFR during non-steady state conditions such as active diuresis and extracellular volume reduction during diuresis, and true GFR measured by lohexol clearance testing has never been studied.
5. The effect of rapid diuresis on cardiac structure and function has not been well studied
6. The short-term effect of rapid volume removal on measures of sleep is unknown

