11.4.2.1 Outcome measures

Key secondary endpoints include weight change, NT-proBNP change, urine output, urine sodium excretion, apnea-hypopnea index, Iohexol glomerular filtration rate, peripheral vein pressure and echocardiographic changes over 24 hours

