1.3 Primary and Secondary Outcomes

- 1.3.1 Primary outcome: urine output at 24 hours after initiation of intravenous diuretic.
- 1.3.2 Secondary outcomes: changes in the following measures over 24 hours after initiation of intravenous diuretic:
 - 1.3.2.1 Body weight
 - 1.3.2.2 NT-proBNP change
 - 1.3.2.3 Urine sodium excretion
 - 1.3.2.4 Apnea-hypopnea index
 - 1.3.2.5 Iohexol glomerular filtration rate
 - 1.3.2.6 Peripheral vein pressure
 - 1.3.2.7 Echocardiographic measures of cardiac output, estimated RV systolic pressure, RA pressure, LA strain, LV and RV global longitudinal strain, E/e'

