1.5 Secondary Analysis

- 1.5.1 Linear regression models will be used to estimate the between group difference in 24-hour change in each of the secondary outcomes; 95% confidence intervals will be constructed using t-based methods.

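### The objective comparing 24-hour creatinine and cystatin C eGFR change with iohexol GFR has no paired analysis, and the SAP outcome lists omit both eGFR changes

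*Combined protocol and SAP*

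**What the plan says.** **The objective.** Section 3.2(c) is "To compare 24 hour change creatinine and cystatin C based changes in GFR with gold standard Iohexol clearance testing of GFR", followed by "among the two diuretic strategies". Section 4.3, item 4, gives the scientific motive: "The relationship between creatinine based GFR during non-steady state conditions such as active diuresis" and its relation to "true GFR measured by lohexol clearance testing has never been studied". That novelty claim concerns creatinine-based GFR and does not mention cystatin C.

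**The analysis.** The Study Summary and Section 4.1 list creatinine and cystatin C eGFR changes and iohexol GFR among the key secondary endpoints, which "will each be compared by T test between the two groups". SAP 1.5 (in Section 11.5.1) says: "Linear regression models will be used to estimate the between group difference in 24-hour change in each of the secondary outcomes".

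**The outcome lists.** In SAP 1.3.2 the only GFR entry is "Iohexol glomerular filtration rate". Section 11.4.2.1 likewise has only iohexol: "apnea-hypopnea index, Iohexol glomerular filtration rate, peripheral vein pressure and echocardiographic changes over 24 hours". Neither list contains an eGFR change.

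**The data.** The Schedule of Events places creatinine, cystatin C and iohexol GFR on both Day 1 and Day 2. Section 8.1.3 has the baseline tests repeated at 24 hours.

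**The concern.** A comparison of an estimating method with a reference method is made inside each patient: how far does the eGFR change depart from the measured change? Testing the arms on each measure separately asks whether treatment moved that measure. Both arm tests could be null while eGFR change is badly wrong in individual patients. One significant and one non-significant arm test would not show that the methods differ.

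The outcome lists raise a separate matter. Taken literally, SAP 1.5 models only what SAP 1.3.2 lists, so the eGFR half of the comparison drops out of the regression plan.

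The result would have a use within this trial. The primary safety endpoint (Study Summary, Section 4.1) and one of the two monitored safety events (Section 10) rest on a decline in estimated GFR over 24 hours. How well eGFR change follows measured GFR change during diuresis bears on how those results are read.

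**Working it through.** **1. The plan's own figure.** SAP 1.7 gives 80% power for a 1688 ml difference in urine output, with SD 1200 ml, two-sided alpha 0.05, 10 per arm and 10% dropout. With 9 evaluable per arm, the noncentral t distribution gives 80.0% at 1688 ml. For 1500 to 2000 ml it gives 70.2, 75.7, 80.5, 84.8, 88.3 and 91.3%, against the stated 70, 75, 80, 84, 88 and 91%. The figure reproduces. It concerns urine output only; the plan states no precision for the GFR comparison.

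**2. Can arm tests tell good agreement from bad?** The documents give no SD for GFR changes and no correlation between methods, so the following values are assumed: SD 10 for each change, 9 per arm, 20,000 simulated trials.

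| Correlation | Bias | Arm effect | Arm test, iohexol | Arm test, eGFR | Paired test of bias |
|---|---|---|---|---|---|
| 0.95 | 0 | 0 | 5.2% | 5.1% | 5.1% |
| 0 | -15 | 0 | 4.9% | 4.9% | 98.9% |
| 0.95 | 0 | -10 | 51.2% | 51.3% | 5.2% |
| 0 | -15 | -10 | 51.0% | 51.9% | 98.8% |

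The arm-test columns are the same, apart from simulation error, whether agreement is close or absent. The percentages depend on the assumed values. The pattern does not: a constant bias cancels in a between-arm difference, and the correlation between methods does not enter either test.

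**3. What could be recovered from arm summaries?** If the same patients contribute to both measures, mean eGFR change minus mean iohexol change equals the mean paired difference. A point estimate of bias, overall or by arm, is therefore available if mean changes are reported. Its uncertainty is not, because

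SDd = √(s₁² + s₂² − 2·r·s₁·s₂)

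needs the within-patient correlation r. With s₁ = s₂ = 10:
- r = 0.95 gives SDd = √10 = 3.16;
- r = 0 gives SDd = √200 = 14.14.

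With 18 pairs the 95% CI half-width for bias would be 0.497 × 3.16 = 1.6 or 0.497 × 14.14 = 7.0. The limits of agreement would be ±1.96 × 3.16 = ±6.2 or ±1.96 × 14.14 = ±27.7. The same reported means fit both cases.

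**4. Precision of a paired analysis, in units of SDd.**
- Mean bias, t(0.975, n−1)/√n: 2.093/√20 = 0.47 with 20 pairs; 2.110/√18 = 0.50 with 18.
- Each limit of agreement, t(0.975, n−1) × √(1/n + 1.96²/(2(n−1))): 2.093 × 0.389 = 0.81 with 20; 2.110 × 0.411 = 0.87 with 18.
- Arm difference in bias, t(0.975, 2m−2) × √(2/m) with m per arm: 2.101 × 0.447 = 0.94 with 10; 2.120 × 0.471 = 1.00 with 9.
- Limits of agreement within one arm: ±1.27 with 10 patients, ±1.37 with 9.

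Pooled estimation is workable. Arm-specific agreement is very imprecise.

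**The case against.** **The objective may be about arms.** It ends by naming the two strategies, and the neighbouring objectives are mostly arm comparisons. If (c) asks only how each strategy moves each GFR measure, the t tests in the Study Summary and Section 4.1 partly answer it. The ambiguity is real. But the reference-standard wording and Section 4.3 favour a method comparison. Asking whether the discrepancy differs by arm would also need the within-patient difference as the outcome, and no section defines it.

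**The plan is not silent on bias.** A reader might infer that it yields no information on bias at all. Step 3 of the working shows otherwise: point estimates can be derived. What is missing is the interval, the limits of agreement and the test.

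**The omission is an inconsistency between lists.** The eGFR changes remain key secondary endpoints in the Study Summary and Section 4.1, so it would be wrong to say that the protocol has abandoned them.

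**Correlations are promised.** SAP 1.10 commits to describing how primary and secondary outcomes correlate. This is a multiplicity remark, it does not reach measures absent from SAP 1.3, and correlation is blind to constant bias.

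**Size and method.** Twenty patients cannot settle agreement, which is why the proposal is estimation only. Limits of agreement are one choice; regressing eGFR change on iohexol change would also address a relationship. Either must be named in advance.

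**Conclusion.** The point holds as a moderate gap in a secondary analysis. On either reading of Section 3.2(c), the plan as written has no valid interval or test for the discrepancy between eGFR change and iohexol GFR change, and no limits of agreement. SAP 1.5 does not cover the two eGFR changes because SAP 1.3.2 does not list them.

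Three stronger inferences are not supported:
- The data are not inadequate: all three measures are scheduled on both days.
- The primary efficacy analysis and its power are not affected.
- Nothing here shows that creatinine eGFR is wrong as a safety measure, only that the plan does not analyse the question.

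The precision figures assume roughly normal paired differences and 18 to 20 complete pairs. Section 8.1.2 makes baseline testing conditional on feasibility, so there could be fewer. SDd itself is unknown, so the figures cannot be turned into GFR units without an assumption.

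**What to change.** 1. Add the 24-hour changes in creatinine eGFR and cystatin C eGFR to Section 11.4.2.1 and SAP 1.3.2, so that they match the Study Summary and Section 4.1.
2. Add a paired analysis to SAP 1.5. For each patient, take the 24-hour eGFR change minus the iohexol GFR change, separately for creatinine and cystatin C. Report pooled mean bias with its 95% CI, and limits of agreement with their CIs. Give the between-arm difference in bias with a CI, labelled descriptive.
3. Name the eGFR equations, and put eGFR and iohexol GFR in the same units with the same body-surface-area indexing. Without this the paired difference cannot be interpreted.
4. Reconcile Section 8.1.2, which calls the test iohexol but also describes an iothalamate injection, so that the reference test is unambiguous.
5. State that the analysis is estimation only, and report the number of complete pairs.

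The cost is SAP wording and a small analysis, with no added visits, samples or patients. It should be fixed before unblinding.

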3.3 Exploratory Objectives

- a) To compare length of hospital stay in the ultrahigh versus usual dose groups
- b) To compare total diuretic use in hospital between the ultrahigh versus usual dose groups
- c) To compare 90-day heart failure rehospitalizations between the ultrahigh versus usual dose groups
- d) To compare creatinine based GFR changes from baseline to day 7 or discharge (whichever is sooner) between ultrahigh versus usual dose groups
- e) To explore proteomic changes in blood and urine between the ultrahigh versus usual dose groups
- f) To examine changes in apnea-hypopnea index between ultrahigh and usual dose groups
- g) To determine daytime and nighttime blood pressure patterns between ultrahigh and usual dose groups
- h) To compare arterial stiffness alterations between ultrahigh and usual dose groups
- i) To explore changes in liver elastography in the ultrahigh versus usual dose groups

4. BACKGROUND AND RATIONALE

4.1 Rationale

Acute decompensated heart failure with volume overload is one of the most common causes of hospitalization and is associated with prolonged lengths of stay and substantial expense. Longer lengths of stay are not only associated with greater expense, but also increase the risk of deconditioning and secondary complications. Furthermore, current diuretic strategies are often associated with little to no weight loss in many patients over their hospital stay likely due to inadequate decongestion.¹ Therefore, there remains an important unmet need to achieve more effective and pragmatic approaches to in hospital diuresis to maximize decongestion in a safe and time-efficient manner.

Randomized trials of in hospital diuretic strategies are limited but the DOSE trial randomized patients to a high versus low dose diuretic strategy and demonstrated a trend to improved decongestion (that did not reach statistical significance) with small transient rises in creatinine without long term risk of complications or renal failure.² More recent data suggested that rises in creatinine during diuresis are actually paradoxically associated with the best outcomes (likely due to it being a marker of effective decongestion), and there was no long term

sequelae of these transient creatinine changes or even more sophisticated markers of tubular injury during diuresis.³ Therefore, small changes in creatinine during more aggressive diuresis are likely not clinically important. Additionally, patients with heart failure generally improve renal function, cardiac output and blood pressure once effectively decongested due to alleviation of renal congestion, relative pericardial restraint, improvement in right heart afterload from reduction in pulmonary artery pressure, and improvement in mitral/tricuspid regurgitation. Moreover, our observational data suggest that very high dose diuretic strategies in decompensated heart failure appears safe. The central hypothesis for this study is that a more aggressive diuretic strategy will result in larger volume and more rapid diuresis without harm. This will have advantages for patient care by simplifying diuretic strategies for decompensated heart failure to potentially a high dose strategy as default diuretic approach, enhance probability of effectively decongesting patients and potentially result in shorter lengths of stay with benefits for patients and healthcare systems. The PI has utilized >50 mg of bumetanide IV equivalents daily as standard of care for practice for management of heart failure patients in the cardiac ICU for the last 2 years (bumetanide bolus followed by 24 hour infusion at 2 mg/hour =>50 mg bumetanide daily) with what appears to be efficacy and safety in observational analyses. The current dose of bumetanide is administered as bolus dosing x2 at less than half of the usual dose utilized in the Mayo CCU by the PI to enhance feasibility and blinding with bolus dosing and will allow formal study of the risks and benefits of this approach in this pilot RCT.

In this pilot study we will therefore compare an ultra-high diuretic strategy with a conventional diuretic strategy in patients with decompensated heart failure with a primary efficacy end point of urine output at 24 hours. The primary safety endpoint will be a decline in serum creatinine estimated GFR by 50% of baseline value at 24 hours. This will be a double-blinded randomized pilot trial of ultra-high dose diuretics (IV bumetanide 12.5 mg bid for 24 hours vs IV furosemide at usual doses (twice the home dose of oral daily diuretic in furosemide equivalents administered bid). New initiation of adjunct diuretics (thiazide, SGLT2 inhibitors, acetazolamide, and spironolactone) will be discouraged during the 24-hour study period. Key secondary endpoints include weight change, NT-proBNP change, urine output, urine sodium excretion, creatinine, and cystatin C estimated GFR changes, apnea-hypopnea index, iohexol glomerular filtration rate, serum and urine proteomic analyses, peripheral vein pressure and echocardiographic changes over 24 hours, estimated GFR at day 7 or discharge (whichever is sooner) will each be compared by T test between the two groups.

4.2 Hypothesis:

Ultrahigh dose diuretic infusion will be associated with greater diuretic response and will not be associated with clinically significant decline in eGFR over 24 hours (defined as decline in creatinine estimated GFR of 50% from baseline at 24 hours).

4.3 Innovation:

1. Ultra-high dose diuretic strategies have not been compared to conventional diuretic strategies in a randomized trial
2. The use of a double-blind strategy will minimize bias in terms of diuretic adjustment and alternative therapies.
3. The measurement of serum and urine biomarkers of renal injury, peripheral vein pressure and echocardiography changes at baseline and at 24 hours will provide novel insight into the hemodynamic, renal, and cardiac response to decongestion.

4. The relationship between creatinine based GFR during non-steady state conditions such as active diuresis and extracellular volume reduction during diuresis, and true GFR measured by lohexol clearance testing has never been studied.
5. The effect of rapid diuresis on cardiac structure and function has not been well studied
6. The short-term effect of rapid volume removal on measures of sleep is unknown
7. Proteomic changes associated with high versus usual dose diuretics will be assessed to evaluate for differential expression of key pathways between the two strategies

4.4 .Significance:

1. The demonstration of safety and efficacy with ultra-high dose diuretic strategy compared to conventional diuretic infusion will be an important safety and preliminary efficacy finding to support a multicenter randomized phase III trial for superiority in relation to clinical outcomes.
2. Delineating mechanisms of hemodynamic benefit to more aggressive decongestion and relationship to renal indices will advance our understanding of human cardiorenal syndrome

4.5 Brief Synopsis of Methods:

- Accrual of 20 patients with decompensated heart failure requiring hospitalization randomized to ultra-high vs conventional dose diuretic arms in a double-blind design over 24 hours. Anticipate 25 patients will be enrolled to accrue 20 patients.
- Baseline assessment of renal lohexol clearance, echocardiography, blood sampling and urine sampling and nocturnal Watch Pat one assessment (apnea-hypopnea index), with all above assessments repeated after 24 hours.
- Follow up phone assessment at 90 days to assess heart failure readmission rates.

